### **13.3 Confidentiality Regarding Study Subjects**

The Investigator must ensure that the privacy of all subjects, including their personal identity and all personal medical information, will always be maintained. Subjects will not be identified by their names, but by an individual identification code (i.e., initials and identification number) in eCRFs and other documents or images transferred to the Sponsor.

---

 Prospective study participants may be unable to provide adequate consent due to medications or the systemic effects of the hemorrhage. In such cases, consent may be obtained from a Legally Authorized Representative, provided this is allowed by the relevant IRB.

---

Personal health information (PHI) may be reviewed for the purpose of verifying data recorded in the eCRFs. The monitor may conduct source document verification on behalf of the Sponsor, the quality assurance unit, or regulatory authorities. PHI will always be treated as confidential.

### **13.4 Participating Institutions and Investigators**

Study sites and Investigators will be selected based on a variety of factors including, but not limited to, experience with endovascular techniques, access to required facilities and equipment, sufficient and adequately trained personnel, and availability of potential subjects. The criteria used for determination will be documented. No other centers/institutions are intended to participate in this study without permission from the relevant regulatory authority.

### **13.5 Agreements**

All Principal Investigators and their Sub-Investigators or Co-Investigators must sign an Investigator Agreement. BlackSwan Inc. (or the authorized CRO) must receive a copy of the signed Investigator Agreements before the study may be started at that institution or devices shipped. Any Investigators joining the study after the site has been initiated may not receive devices or participate until an agreement is signed and received by the Sponsor.

### **13.6 Responsibilities**

Investigator responsibilities include, but are not limited to, the following:

1. Conducting the study in accordance with this investigational plan, signed agreement, and applicable regulations protecting the rights and safety of study subjects;
2. Informing all subjects that the device being utilized is for investigational purposes only, and ensuring that the requirements relating to obtaining informed consent and IRB approval are met;
3. Ensuring that informed consent is obtained for each study subject in accordance with applicable regulations (e.g., ISO 14155-1, 21 CFR Part 50);
4. Ensuring that IRB approval is secured prior to starting the study and ensuring continuing review and approval as required throughout the investigation;
5. Ensuring all associates, colleagues, and employees assisting in the conduct of the study are informed about their obligations, are adequately qualified and trained, and meet their commitments;
6. Maintaining adequate and accurate records and ensuring those records are available for inspection at any time;
7. Ensuring that conducting the study does not give rise to conflict of interest (financial disclosure is required);

8. Controlling of all investigational devices under investigation.

## 14 DATA SECURITY AND SCIENTIFIC INTEGRITY

### 14.1 Access to Data

The Sponsor, auditors, and health authority inspectors (or their agents) will be given access to source data and documentation (e.g., medical charts/records, laboratory test results, printouts, videotapes, etc.) for source data verification, provided that subject confidentiality is maintained in accordance with local requirements.

The Investigator must always maintain the primary records (source documentations) of each subject's data. Examples of source documents are hospital records, office visit records, examining physician's finding or notes, consultant's written opinion or notes, laboratory reports, device inventory, device label records, and eCRFs that are used as the source.

The Investigator will maintain a confidential subject identification list that allows the unambiguous identification of each subject. All study-related documents must be kept until notification by BlackSwan Vascular Inc.

### 14.2 Security and Confidentiality

The Investigator must ensure that the privacy of all subjects, including their personal identity and all personal medical information, will always be maintained. In eCRFs and other documents or image material submitted to the Sponsor, subjects will not be identified by their names, but by an identification code (i.e., subject number).

Personal medical information may be reviewed for the purpose of verifying data recorded in the eCRFs. The monitor may perform source data verification on behalf of the Sponsor or regulatory authorities. Personal medical information will always be treated as confidential.

## 15 RISK BENEFIT ANALYSIS

### 15.1 Risks to the Subjects

Treatment with the Lava LES is may pose significant risks to the subject, although these risks are not expected to be greater than with the current standard of care for treatment of bleeding peripheral vessels. A summary of some of the known risks are identified in **Table 8**, below; however, there may be risks that are not known or are unforeseen at this time. The risks include those related to the device and to the procedure, including those related to concomitant medications used periprocedurally and during follow-up.

There are other health risks and discomforts associated with the testing that patients will undergo before and after their procedure, including, but not limited to, bruising during blood collection, pain and bruising at the access site and radiation exposure during imaging procedures.

**Table 8. Known risks of peripheral artery embolotherapy**

Event Category	Event
Vascular	Vessel perforation
	False aneurysm
	Arterial dissection
	Mural thrombus formation
	Vessel occlusion, thrombotic or otherwise
	Arteriovenous fistula
	Distal atheroembolism
	Inadvertent embolization of a non-target vessel or territory
Access site	Infection
	Pain at site
	Serous drainage
	Lymphorrhea
	Hematoma
	Ecchymosis
Cardiac	Myocardial infarction
	Congestive heart failure
	Arrhythmia
	Valve disorders; stenosis and insufficiency
	Hypertension
	Hypotension
Venous	Deep venous thrombosis
	Pulmonary embolism

**Table 8. Known risks of peripheral artery embolotherapy**

Event Category	Event
	Paradoxical embolization
Local	Leg edema
	Leg pain
	Back pain
Cerebrovascular	Transient ischemic attack
	Stroke
	Intracranial hemorrhage
Genitourinary	Urinary retention
	Urinary tract infection
	Renal stones
	Renal insufficiency, failure
	Hematuria
	Impotence and other disorders of sexual function
Pulmonary	Exacerbation of chronic lung disease
	Pneumonia
	Respiratory failure
	Bronchitis
	Bronchospasm
Gastrointestinal	Peptic ulcer disease
	Reflux esophagitis
	Nausea and vomiting
	Diarrhea
	Constipation
	Hepatitis
	Hepatic insufficiency

**Table 8. Known risks of peripheral artery embolotherapy**

Event Category	Event
	Cholelithiasis / cholecystitis
Metabolic/systemic disorders	Electrolyte imbalances
	Hyperglycemia
	Hypoglycemia
	Fluid overload
	Dehydration
	Thrombocytopenia
	Leukopenia
	Anemia with or without need for transfusion
Device-related	Myoglobinemia, myoglobinuria
	Embolization of device components
	Loss of device components within vascular tree
	Inability to extract device from vascular tree
	Allergic reactions to device components
Miscellaneous	Allergic reactions to concomitant medications
	Sepsis
	Psychiatric disorders including depression
	Mental status changes
	Insomnia

## 15.2 Risk Mitigation

The Sponsor designed the Lava LES and the Protocol to minimize risks to the study participants. Study eligibility criteria were formulated to limit use of the study device to subjects and Target Lesions that fit the device specifications. Evaluation of safety data by an independent CEC and DSMB and assessment of imaging studies by an independent core laboratory will provide an ongoing assessment of safety-related events, both individually and in aggregate.

### **15.3 Benefit to Subjects**

It is hoped that the Lava LES will provide additional treatment options for percutaneous treatment of subjects with hemorrhage from peripheral vessels. The avoidance of an open surgical procedure is advantageous in these often very ill patients.

### **15.4 Study Justification**

This study is justified considering previous work showing benefit obtained using embolotherapy for bleeding from peripheral vessels. Despite reports of widespread use and acceptance, to date, the use of marketed liquid embolic agents has not been approved for use in the peripheral vessels the United States. This study will attempt to build on past results with other agents and devices and, potentially, identify additional benefits of liquid embolic agent Lava for the treatment of bleeding peripheral vessels. The objective evaluation of the study device will be assured through the performance of a clinical trial that uses a standardized protocol, pre-specified endpoints and statistical testing, an adequate sample size in appropriate study population, independent CEC and DSMB committees, and an independent core laboratory, and clinical site monitoring of original source documents.

## **16 ELECTRONIC DATA COLLECTION**

An EDC will be used in this study for recording data. Where entries in the EDC are not based upon the subject's medical record, worksheets can be utilized but each must be signed and dated by the site's Principal Investigator. The medical record and the signed and dated worksheets will comprise the original source documentation. Where discrepancies exist between the medical record and worksheets, information in the medical record will prevail.

Source documents will be verified for alignment with EDC fields. There will be 100% source document verification in this trial; all EDC fields will be checked against information in the source documents.

## 17 ABBREVIATIONS

The following abbreviations are used in this document:

Abbreviation	Description
AVF	Arteriovenous fistula
CC	Completed cases
CEC	Clinical events committee
CRO	Contract research organization
cSt	Centistoke
DMSO	Dimethyl sulfoxide
DSMB	Data and safety monitoring board
eCRF	Electronic case report form
EDC	Electronic data collection
FDA	Food and Drug Administration
ICF	Informed consent form
ICU	Intensive care unit
INR	International normalization ratio
IRB	Institutional review board
ITT	Intent to treat
LAR	Legally authorized representative
LES	Liquid Embolic System
LGIB	Lower gastrointestinal bleed
MAE	Major adverse event
PHI	Personal Health Information
PSA	Pseudoaneurysm
PVA	Polyvinyl alcohol
SAE	Serious Adverse Event
SAP	Statistical Analysis Plan
SIR	Society of Interventional Radiology

SIV	Site initiation visit
SOP	Standard Operating Procedures
UADE	Unanticipated adverse device effect
UGIB	Upper gastrointestinal bleed

## 18 DEFINITIONS

Category	Term	Definition
BARC Bleeding	Types 0 – 2 (do not trigger endpoint)	
Type 0: no bleeding
 
Type 1: bleeding that is not actionable and does not cause the patient to seek unscheduled performance of studies, hospitalization, or treatment by a healthcare professional; may include episodes leading to self-discontinuation of medical therapy by the patient without consulting a healthcare professional
 
Type 2: any overt, actionable sign of hemorrhage (eg, more bleeding than would be expected for a clinical circumstance, including bleeding found by imaging alone) that does not fit the criteria for type 3, 4, or 5 but does meet at least one of the following criteria: (1) requiring nonsurgical, medical intervention by a healthcare professional, (2) leading to hospitalization or increased level of care, or (3) prompting evaluation.

	Types 3 – 5 (endpoint trigger)	
Type 3: Clinical, laboratory, and/or imaging evidence of bleeding with specific healthcare provider responses, as listed below:
 
Type 3a:
 
 
• Overt bleeding plus hemoglobin drop of <math>\geq 3</math> to <math><5</math> g/dL* (provided hemoglobin drop is related to bleed)
 
• Overt bleeding plus hemoglobin drop 3 to 5 g/dL, (provided hemoglobin drop is related to bleeding). Hemoglobin drop should be corrected for intracurrent transfusion in which 1 U packed red blood cells or 1 U whole blood would be expected to increase hemoglobin by 1 g/dL.
 
 
Type 3b:
 
 
• Overt bleeding plus hemoglobin drop <math>\geq 5</math> g/dL, provided hemoglobin drop is related to bleed). Hemoglobin drop should be corrected for intracurrent transfusion in which 1 U packed red blood cells or 1 U whole blood would be expected to increase hemoglobin by 1 g/dL.
 
• Cardiac tamponade
 
• Bleeding requiring surgical intervention for control (excluding dental/nasal/skin/hemorrhoid)
 

Category	Term	Definition
		
 
• Bleeding requiring intravenous vasoactive drugs
 
 
Type 3c:
 
 
• Intracranial hemorrhage (does not include microbleeds or hemorrhagic transformation; does include intraspinal); subcategories confirmed by autopsy, imaging, or lumbar puncture
 
• Intraocular bleed compromising vision
 
 
Type 4: Coronary artery bypass-related bleeding; not applicable.
 
Type 5: Fatal bleeding is bleeding that directly causes death with no other explainable cause. The site of fatal bleeding is specified as intracranial, gastrointestinal, retroperitoneal, pulmonary, pericardial, genitourinary, or other. BARC fatal bleeding is categorized as either definite or probable as follows:
 
Type 5a:
 
Probable fatal bleeding (type 5a) is bleeding that is clinically suspicious as the cause of death, but the bleeding is not directly observed and there is no autopsy or confirmatory imaging.
 
Type 5b:
 
Definite fatal bleeding (type 5b) is bleeding that is directly observed (by either clinical specimen such as blood, emesis, stool or imaging) or confirmed on autopsy.

Clinical Success		Absence of bleeding in a Target Lesion after embolization with the Lava LES and any adjunctive devices employed during the index procedure, without the need for emergency surgery, re-embolization, or other target territory reinterventions within 30 days of the index procedure.
Device-Related Events		
Device-related events constitute those events that are deemed directly attributable to the Lava LES itself.
 
Catheter entrapment will be considered a device-related adverse event, as will rebleeding after the index procedure. Continued bleeding, i.e. failure of the Lava LES to arrest hemorrhage, will constitute failure of the effectiveness endpoint but is not an adverse event, in and of itself.
 
An event that is related to a prior device-related event is also considered to be device-related.

Hemorrhage	Bleeding	Bleeding is defined with respect to the Investigator-assigned

Category	Term	Definition
		target territories. Bleeding outside of a target territory is not tabulated in the primary or secondary endpoints, except for access site bleeding which is not tabulated in the primary endpoint but is included in the secondary access-site endpoints.

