## 5.3 Secondary Endpoints

The following measures will be assessed as secondary endpoints of the study:

1. Technical Success, defined as absence of angiographic evidence of bleeding from the target lesion at the conclusion of the index procedure;
2. Successful delivery of Lava and intact retrieval of the microcatheter;
3. Assessment of each element of the primary safety endpoint (MAE) as an individual component;
4. Symptomatic ischemia in the target territory that does not require intervention;
5. All-cause mortality;
6. Bleeding-related mortality (attributable to bleeding in a target territory);
7. Open surgical conversion for persistent or recurrent bleeding;
8. Device-related serious adverse events;
9. Procedure-related serious adverse events;
10. Access site hematoma (>5cm in longest axis);c
11. Access site false aneurysm;
12. Units of red blood cells transfused after administration of Lava;

a The effectiveness endpoint is lesion-based and not subject-based. Failure of the effectiveness endpoint is triggered by events that are referable to the specific lesion and not to other events referable to another lesion in the same subject. For example, if a subject has two lesions where the first is treated successfully but the other rebleeds and requires emergency surgery, effectiveness would have been achieved in the first lesion but not in the second.

b Core laboratory-determined assessment of bleeding is used for the primary and secondary endpoints. If core laboratory images are unavailable or uninterpretable, the site-reported determinations will be used.

c As measured on a duplex ultrasound study, assessed by the Core Laboratory.

- 13. Duration index procedure, total and after administration of Lava;
- 14. Contrast administered during index procedure;
- 15. Fluoroscopy time during index procedure;
- 16. Length of stay in the intensive care unit after the index procedure;
- 17. Length of hospitalization, total and after the index procedure.

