	Catheter breakage	Breakage of the catheter used to deliver Lava, resulting in a luminal catheter defect at the portion of the catheter that resided within the subject's vasculature. Kinks are not considered breakage. Breaks of other catheters, sheaths, and guides do not trigger this component of the composite MAE endpoint.
	Catheter entrapment	Inability to extract the catheter used for Lava delivery, due to adherence to the Lava material, requiring endovascular or open surgical intervention to remove the catheter or retained pieces of the catheter. The endpoint is triggered if pieces of the catheter are retained in the subject's vasculature at the conclusion of the index procedure.
Non-Target Territory		A vascular territory outside of the planned Target Territory specified by the Investigator prior to embolization at that site. Inadvertent embolization of Lava to a Non-Target Territory is an element of the composite MAE endpoint.
Procedure-Related		A procedure-related event is an event that occurs during the index procedure or within 30 days of the index procedure-irrespective of causation but not otherwise classified as a device-related event (i.e. an event that is device-related need not also be reported as procedure-related). As well, procedure-related adverse events include any events related to a remedial procedure necessary to treat the target territory (e.g. a rebleeding episode). An event related to a prior procedure-related event is also considered to be procedure-related.
Reintervention		Defined as those secondary procedures, endovascular or open surgical, that occur after the subject has left the angiography suite after the index procedure and are performed as a result of residual bleeding, recurrent bleeding, or a device- or procedure-related events.
Serious Adverse Event		An adverse event where the outcome is one of the following: 1. Death; 2. Life-threatening, where the patient was at substantial

Category	Term	Definition
		
risk of dying or continued use of the product might have resulted in death;
 
 
3. Hospitalization or prolongation of an existing hospitalization;
 
4. Disability or permanent damage, interfering with the patient's ability to conduct normal life functions;
 
5. Congenital anomaly or birth defect;
 
6. Required intervention to prevent permanent impairment.
 

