1. Technical Success, defined as absence of angiographic evidence of bleeding from the target lesion at the conclusion of the index procedure;
2. Successful delivery of Lava and intact retrieval of the microcatheter;
3. Assessment of each element of the primary safety endpoint (MAE) as an individual component within 30 days of the index procedure;
4. Symptomatic ischemia in the target territory that does not require intervention within 30 days of the index procedure;
5. All-cause mortality within 30 days of the index procedure;
6. Bleeding-related mortality (attributable to bleeding in a target territory) within 30 days of the index procedure;
7. Open surgical conversion for persistent or recurrent bleeding within 30 days of the index procedure;
8. Device-related serious adverse events within 30 days of the index procedure;
9. Procedure-related serious adverse events within 30 days of the index procedure;

 The effectiveness endpoint is lesion-based and not subject-based. Failure of the effectiveness endpoint is triggered by events that are referable to the specific lesion and not to other events referable to another lesion in the same subject. For example, if a subject has two lesions where the first is treated successfully but the other rebleeds and requires emergency surgery, effectiveness would have been achieved in the first lesion but not in the second.

 Core laboratory-determined assessment of bleeding is used for the primary and secondary endpoints. If core laboratory images are unavailable or uninterpretable, the site-reported determinations will be used.

10. Access site hematoma (>5cm in longest axis) within 30 days of the index procedure;
11. Access site false aneurysm within 30 days of the index procedure;
12. Units of red blood cells transfused after administration of Lava;
13. Duration of the index procedure, total and after administration of Lava;
14. Contrast administered the during index procedure;
15. Fluoroscopy time during the index procedure;
16. Length of stay in the intensive care unit after the index procedure;
17. Length of hospitalization, total and after the index procedure.

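### Read literally, Section 18's rule on bleeding outside a target territory conflicts with the procedure-related SAE endpoint and could undercount it

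*Protocol*

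**What the plan says.** The entry for bleeding in Protocol Section 18 opens "Bleeding is defined with respect to the Investigator-assigned" target territories. It continues: "Bleeding outside of a target territory is not tabulated in the primary or secondary endpoints, except for access site bleeding". Access-site bleeding is kept out of the primary endpoint but "is included in the secondary access-site endpoints".

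The secondary endpoints in Protocol 5.3 include item 8, "Device-related serious adverse events", and item 9, "Procedure-related serious adverse events". Both reappear as items 6 and 7 of Protocol 7.5. In SAP Section 2 they are items 8 and 9, the latter worded "Procedure-related serious adverse events within 30 days of the index procedure". None of these lists limits the SAE endpoints by organ, territory or type of event.

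Section 18 defines relatedness broadly: "A procedure-related event is an event that occurs during the index procedure or within 30 days of the index procedure-irrespective of causation", provided the event is not already classed as device-related. Device-related is narrower. It requires direct attribution to the Lava LES, but later events that stem from a device-related event inherit the label, and catheter entrapment is expressly device-related.

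Protocol Section 4 says the safety evaluation covers complications at the insertion site, along the access route and at the site of administration. Table 8 lists "Vessel perforation" among the known vascular risks.

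**The concern.** A territory limit is sensible for asking whether the treated lesion rebled. It does not suit an SAE count, whose purpose is to capture serious harm wherever it occurs. In a trial of an embolic agent for hemorrhage, a serious bleed caused by the procedure away from the lesion is a central harm.

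The SAE endpoints are the main pre-specified place for a non-fatal bleed of this kind. None of the five MAE components is bleeding or perforation, Clinical Success concerns the target lesion, and bleeding-related mortality is confined to target territories. If Section 18 also governs the SAE endpoints, a serious pathway bleed would have no endpoint, although Section 4 promises to evaluate pathway complications.

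**Working it through.** There is no stated figure to reproduce. The check sets the passages side by side and then shows what an omission would do to a reported rate.

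**Step 1. Apply both rules to the same events.** Each event is assumed to be serious under Protocol 10.1 and to occur in an enrolled subject within 30 days.

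| Event | Endpoint lists and relatedness definitions | Section 18 bleeding sentence, read literally |
|---|---|---|
| Bleed from a non-target vessel injured by wire or catheter | Procedure-related SAE | Not tabulated |
| Bleed outside the target territory following catheter entrapment | Device-related SAE, through the inherited label | Not tabulated |
| Access-site bleed, neither hematoma over 5 cm nor false aneurysm | Procedure-related SAE | Excepted from the bar and sent to the access-site endpoints, whose criteria it does not meet; SAE endpoints not mentioned |
| Bleed inside a target territory | Device- or procedure-related SAE | Tabulated; no conflict |

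The first row is a direct contradiction. The second is the same contradiction by a rarer route, since an ordinary wire or catheter injury is not directly attributable to the Lava LES. The third is a gap: the text does not settle the matter either way.

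**Step 2. See whether the SAP resolves it.** Protocol 7.12 says the SAP details all analyses. SAP 2 lists both SAE endpoints without the exclusion. It does not define bleeding or relatedness and does not set Section 18 aside, so whoever programs the endpoints must go back to the protocol definitions.

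**Step 3. Size per omitted subject.** Safety endpoints are subject-level in the ITT set (Protocol 7.6). With the planned 113 subjects, dropping one whose only qualifying SAE was such a bleed lowers the rate by 1/113 = 0.88, or about 0.9 percentage points.

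**Step 4. How often it could arise.** The documents give no rate for these bleeds, so the true rates p below are assumptions. Expected number = 113p; chance of at least one = 1 − (1 − p)^113.

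| Assumed p | Expected number | Chance of at least one |
|---|---|---|
| 0.5% | 0.57 | 43% |
| 1% | 1.13 | 68% |
| 2% | 2.26 | 90% |
| 3% | 3.39 | 97% |

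**Step 5. The importance depends on the base rate, also assumed.** Suppose two subjects are omitted.

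- If they were the only subjects with a qualifying SAE, 2/113 = 1.77% (exact 95% interval 0.22% to 6.25%) becomes 0/113 = 0% (0% to 3.21%).
- If 30 subjects had a qualifying SAE, 30/113 = 26.5% becomes 28/113 = 24.8%.

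The absolute change is the same, 1.77 points. The first case is the extreme. Because the procedure-related definition ignores cause and Protocol 10.1 counts prolonged hospitalization as serious, a base rate near zero is unlikely.

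**The case against.** The best answer is that the sentence was never meant to reach SAEs. It sits in the entry that defines bleeding, next to absence of bleeding, recurrent bleeding and persistent bleeding, the terms that feed the bleeding endpoints. The SAE and procedure-related entries stand apart and carry no territory limit. The footnote to exclusion criterion 8 draws the same line: rebleeding from extra lesions treated with non-study agents does not count against effectiveness, yet complications there are procedure-related. On this reading there is no conflict.

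That reading is reasonable, and may be what was intended, but it is not written down. The sentence names the primary and secondary endpoints without qualification, makes one exception, and does not mention SAEs. Two careful programmers could produce different counts.

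Four further points stand and limit the concern.

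- A reader might infer that all bleeding outside a target territory is barred from every endpoint. It is not: access-site bleeding is excepted. Nor does the text say that access-site bleeding goes to the access-site endpoints alone.
- A reader might infer that events are lost. They are not. Protocol 10.2 requires every adverse event to be reported and treats events between arterial access and Lava administration as procedure-related. The Medical Monitor reviews every adverse event (10.3), and SAP 3.4.4 tabulates them by severity and relationship. These tables are not the endpoint, however; the exact interval in SAP 3.4.3 attaches to the endpoint rate, which could then disagree with the tables.
- Perforation is its own event in Table 8, so a serious perforation might be counted even under the literal rule. The count would then depend on which term the site chose.
- The device-related endpoint is reached only indirectly, as in Step 1.

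**Conclusion.** The conflict is real and lies in the wording. Read literally, Section 18 excludes from the procedure-related SAE endpoint serious bleeds that the endpoint's own definition includes, and it sits badly with the aim in Section 4. The device-related endpoint is affected only through events that follow from a device-related one, and the treatment of some serious access-site bleeds is undefined.

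The consequence is a possible undercount in descriptive secondary rates, 0.9 points per omitted subject out of 113. This assumes that the literal reading is applied, that the bleed is the subject's only qualifying SAE, and that all 113 subjects are evaluable. How many subjects would be affected cannot be derived from the documents.

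The documents do not support a claim that a known share of SAEs will disappear, or that the trial's conclusion is at risk. Study success rests on Clinical Success, which is lesion-based by design, and on freedom from MAE, which has no bleeding component. No hypothesis is tested on the secondary endpoints (SAP 3.4.1).

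**What to change.** In Protocol Section 18, limit the sentence to the bleeding-specific endpoints: Clinical Success, persistent or recurrent bleeding, and bleeding-related mortality. State there and in SAP Section 2 (items 8 and 9) that the device- and procedure-related SAE endpoints count every bleed that meets the seriousness and relatedness definitions, at any site, including the catheter pathway and the access site. Say also that an access-site bleed may count both in an access-site endpoint and as an SAE.

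The cost is about one sentence in each document. Sample size, alpha, power and data collection do not change. The reported SAE rate may be slightly higher.
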